Each affiliate site will be responsible for safety reporting to their local IRB. Investigators are responsible for complying with their local IRB's reporting requirements, though must submit the required reports to their IRB no later than 7 calendar days following the occurrence of the UP or the Principal's Investigator's acquiring knowledge of the UP. Copies of each report and documentation of IRB notification and receipt must be included in the regulatory binder.

Expected AEs must be reported at the time of continuing review of a protocol.

Guidelines for Processing IND Safety Reports

The U.S. Food and Drug Administration (FDA) regulations require sponsors of clinical studies to notify the FDA and all participating investigators of any serious and unexpected adverse experiences that are possibly related to the investigational agent. The CUMC Principal Investigator will review all applicable IND Safety Reports and has the responsibility for forwarding the IND Safety Reports to the Affiliate Institutions. The Affiliate Institution investigators are to review, send a copy to their IRB according to their local IRB's policies and procedures, and file a copy with their regulatory documents. All Affiliate site INDSR submissions, along with IRB acknowledgment (per local policies and procedures) are to be forwarded to CUMC for placement within the trial master file.

Reporting to Hospital Risk Management

Affiliate Site investigators will report to their local Risk Management Office any subject safety reports or sentinel events that require reporting according to institutional policy.

9. Confidentiality

Each affiliate site will be assigned a site number. Each subject that signs consent should be assigned a unique code number consisting of site number followed by a number with each new subject being assigned the next sequential number (e.g., 04-10). All sites will be required to enter their data in the Velos eResearch, the Clinical Trial Management System used for all Cancer-related clinical research at CUMC. All users must login with their own application username and password. Users off campus must first access the Virtual Private Network with their assigned campus username and password and then use their application credentials.

Subject confidentiality must be maintained according to HIPAA regulations and GCP recommendations.

Except when required by law, study information shared with persons and organizations outside of Columbia University Medical Center must not identify the patient by name, social security number, address, telephone number, or any other direct personal identifier.

If the results of this research project are published or presented at a scientific or medical meeting, the patient not be identified. Otherwise, all results will be kept confidential and will not be divulged (except as required by law) without permission.

10. Data Reporting Plan

Columbia University Medical Center (CUMC) is deeply committed to research integrity and strong credibility when it comes to the discovery of new treatment concepts, implementation of new clinical research techniques, and acceptance of its researcher's findings by the medical establishment. In accord with these ethics, CUMC encourages and supports its investigators in the sharing of final research data and/or details of newly developed clinical treatments.

CUMC's policies that pertain to patient data sharing conform to CUMC IRB rules, local and state laws, and HIPAA privacy regulations. The primary reason for this is to protect the privacy of patients who participate in clinical trials. The data can be made available for continuing review by federal agencies upon request and for ongoing study safety reviews by the Principal Investigator, Statistician, Data Safety and Monitoring Board (DSMC), and, in other instances, the CUMC IRB.

Data collected during the course of this clinical trial will primarily be shared with other investigators and University staff, the IRB, FDA, and other reporting agencies, and/or transferred to other collaborators. Prior to transfer, the data collected must comply with, and must be limited by, the CUMC's guidelines for Protecting the Rights and Privacy of Human Subjects.

11. Data Acquisition and Submission

Informed consent, including HIPPA authorization, must be obtained on all subjects prior to their participation. Always keep the original signed and dated consent form, with the redacted source documents and eligibility checklist. Velos eResearch will be used as the electronic clinical trials and data management system. Affiliate sites will enter data directly into Velos eResearch via customized case report forms for the study. The research staff will generate reports from Velos eResearch to ensure timely submission of data by affiliate sites. This resource allows for the timely analysis of particular data sets for safety analysis.

12. Record Keeping and Record Retention

The Principal Investigator is required to maintain adequate records of the disposition of the drug, including dates, quantity, and use by subjects, as well as written records of the disposition of the drug when the study ends.

The Principal Investigator is required to prepare and maintain adequate and accurate case histories that record all observations and other data pertinent to the investigation on each individual administered the investigational drug or employed as a control in the investigation. Case histories include the case report forms and supporting data including, for example, signed and dated consent forms and medical records including, for example, progress notes of the physician, the individual's hospital chart(s), and the nurses' notes. The case history for each individual shall document that informed consent was obtained prior to participation in the study. Study documentation includes all CRFs, data correction forms or queries, source documents, Sponsor-Investigator correspondence, monitoring logs/letters, and regulatory documents (e.g., protocol and amendments, CHR correspondence and approval, signed patient consent forms). Source documents include all recordings of observations or notations of clinical activities and all reports and records necessary for the evaluation and reconstruction of the clinical research study. In accordance with FDA regulations, the investigator shall retain records for a period of 2 years following the date a marketing application is approved for the drug for the indication for which it is being investigated; or, if no application is to be filed or if the application is not approved for such indication, until 2 years after the investigation is discontinued and FDA is notified.

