6.14. Women must not be pregnant or breastfeeding

6.15. WOCBP must agree to follow instructions for method(s) of contraception for the duration of study treatment with nivolumab and 5 months after the last dose of study treatment (i.e., 30 days (duration of ovulatory cycle) plus the time required for the investigational drug to undergo approximately five half-lives.)

6.16. Males who are sexually active with WOCBP must agree to follow instructions for method(s) of contraception for the duration of study treatment with nivolumab and 7 months after the last dose of study treatment (i.e., 90 days (duration of sperm turnover) plus the time required for the investigational drug to undergo approximately five half-lives.)

6.17. Azoospermic males are exempt from contraceptive requirements. WOCBP who are continuously not heterosexually active are also exempt from contraceptive requirements, but still must undergo pregnancy testing as described in this section.

6.18. Investigators shall counsel WOCBP, and male participants who are sexually active with WOCBP, on the importance of pregnancy prevention and the implications of an unexpected pregnancy. Investigators shall advise on the use of highly effective methods of contraception, which have a failure rate of $< 1\%$ when used consistently and correctly.

6.19. At a minimum, participants must agree to use 1 highly effective method of contraception as listed in Appendix 2.

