20.2 Appendix 2: Methods of Contraception

At a minimum, subjects must agree to use one highly effective method of contraception as listed below:

HIGHLY EFFECTIVE METHODS OF CONTRACEPTION

Highly effective methods of contraception have a failure rate of < 1% when used consistently and correctly. WOCBP and female partners of male subjects, who are WOCBP, are expected to use one of the highly effective methods of contraception listed below. Male subjects must inform their female partners who are WOCBP of the contraceptive requirements of the protocol and are expected to adhere to using contraception with their partner. Contraception methods are as follows:

- 1) Progestogen only hormonal contraception associated with inhibition of ovulation.
- 2) Hormonal methods of contraception including oral contraceptive pills containing combined estrogen + progesterone, vaginal ring, injectables, implants and intrauterine devices (IUDs) such as Mirena®
- 3) Nonhormonal IUDs, such as ParaGard®
- 4) Bilateral tubal occlusion
- 5) Vasectomised partner with documented azoospermia 90 days after procedure
 - Vasectomised partner is a highly effective birth control method provided that partner is the sole sexual partner of the WOCBP trial participant and that the vasectomized partner has received medical assessment of the surgical success.
- 6) Intrauterine hormone-releasing system (IUS).
- 7) Complete abstinence
 - Complete abstinence is defined as the complete avoidance of heterosexual intercourse (refer to Glossary of Terms)
 - Complete abstinence is an acceptable form of contraception for all study drugs and must be used throughout the duration of the study treatment (plus approximately 5 half-lives of the investigational drug plus 30 days).
 - It is not necessary to use any other method of contraception when complete abstinence is elected.
 - Subjects who choose complete abstinence must continue to have pregnancy tests, as specified in Section 12.
 - Acceptable alternate methods of highly effective contraception must be discussed in the event that the subject chooses to forego complete abstinence.
 - The reliability of sexual abstinence needs to be evaluated in relation to the duration of the clinical trial and the preferred and usual lifestyle of the subject.

UNACCEPTABLE METHODS OF CONTRACEPTION

- 1) Periodic abstinence (calendar, symptothermal, post-ovulation methods)
- 2) Withdrawal (coitus interruptus)

- 3) Spermicide only
- 4) Lactation amenorrhea method (LAM)

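### Appendix 2 gives complete abstinence a single period, the women's formula, which for men is 60 days shorter than the formula in item 6.16

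*Combined protocol and SAP*

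**What the plan says.** The inclusion criteria (section 6.1) set the contraception period by sex.

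- **Women, item 6.15.** Study treatment plus 5 months after the last dose, explained as "30 days (duration of ovulatory cycle) plus the time required for the investigational drug to undergo approximately five half-lives".
- **Men sexually active with WOCBP, item 6.16.** Study treatment plus "7 months after the last dose of study treatment (i.e., 90 days (duration of sperm turnover"), again with about five half-lives added.
- **Exemptions, item 6.17.** Azoospermic men are exempt. On abstinence, the item speaks only of women: "WOCBP who are continuously not heterosexually active are also exempt from contraceptive requirements". It gives no rule or period for an abstinent man.
- **Link to the appendix, item 6.19.** At a minimum, "participants must agree to use 1 highly effective method of contraception as listed in Appendix 2". This is addressed to participants of both sexes.

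Appendix 2 (section 20.2) then lists the acceptable methods. Its introduction covers men: "Male subjects must inform their female partners who are WOCBP of the contraceptive requirements of the protocol", and they are expected to keep to contraception with that partner. Under method 7, complete abstinence "must be used throughout the duration of the study treatment (plus approximately 5 half-lives of the investigational drug plus 30 days"). The same entry adds: "It is not necessary to use any other method of contraception when complete abstinence is elected". No 90-day or 7-month period appears anywhere in Appendix 2.

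**The concern.** The abstinence entry carries the women's formula into a list that men are also told to use. A man who is sexually active with a WOCBP when he enters, and who chooses abstinence as his method, meets two periods. Item 6.16 tells him 7 months. The appendix tells him about 5 half-lives plus 30 days, and that he needs no other method. Appendix 2 is the only place where a period is attached to abstinence itself, so a site looking up that method will find the shorter figure.

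What is at stake is a safety period that, as written for men, ends before the sperm-turnover interval behind item 6.16 has run. The written text carries some weight because the gap falls after the scheduled safety visits. With follow-up visit X01 at day 35 after the last dose, X02 falls at about day 35 + 80 = 115 (Table 12.3). Later contacts are every 3 months, may be by telephone, and are for survival and subsequent therapy. Nothing here bears on efficacy.

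**Working it through.** **Inputs**

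- Elimination half-life: geometric mean 26.7 days (section 4.3, Clinical Pharmacokinetics).
- Women: 30 days + about 5 half-lives, stated as 5 months (item 6.15).
- Men: 90 days + about 5 half-lives, stated as 7 months (item 6.16).
- Complete abstinence, sex not specified: about 5 half-lives + 30 days (Appendix 2, method 7).
- Conversion: 1 month = 365.25 / 12 = 30.44 days.

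**Step 1. Do the stated months follow from the formulas?**

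- Five half-lives: 5 × 26.7 = 133.5 days.
- Women: 133.5 + 30 = 163.5 days; 163.5 / 30.44 = 5.4 months (stated: 5).
- Men: 133.5 + 90 = 223.5 days; 223.5 / 30.44 = 7.3 months (stated: 7).

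An assumed half-life of 25 days gives 155 days (5.1 months) and 215 days (7.1 months). The stated 5 and 7 months are therefore rounded versions of the formulas, and neither is in dispute.

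**Step 2. Compare the Appendix 2 period with the men's period.**

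| Source | Formula | Days after last dose |
|---|---|---|
| Appendix 2, abstinence | 5 × 26.7 + 30 | 163.5 |
| Item 6.15, women | 5 × 26.7 + 30 | 163.5 |
| Item 6.16, men | 5 × 26.7 + 90 | 223.5 |

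For women, the appendix and the criterion agree. For men, the difference is 223.5 − 163.5 = 60 days. The half-life term cancels, leaving 90 − 30 = 60 at any half-life.

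**Step 3. Cross-check against the stated months.**

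- 7 months − 5 months = 213.1 − 152.2 = 60.9 days, consistent with 60.
- The unrounded Appendix 2 formula against the rounded 7 months: 213.1 − 163.5 = 49.6 days. This is the smallest reading of the gap. It mixes an unrounded with a rounded figure, so the 60-day comparison of formula with formula is the cleaner one.

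**Step 4. Does the abstinence entry reach men?** Item 6.19 sends participants, not only women, to Appendix 2. The introduction to the appendix names male subjects and gives them duties. Nothing in method 7 limits the period to women.

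**The case against.** The strongest reply is that the abstinence entry was written for women. A neighbouring bullet requires subjects who choose abstinence to go on having pregnancy tests, and section 12 restricts those tests to WOCBP. The 30-day term is the ovulatory-cycle term. On that reading the bullet simply repeats item 6.15, correctly. This is a plausible account of where the text came from. It does not remove the problem, because the wording is not limited to women and the appendix expressly includes men.

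The second reply is that the two texts can mostly be followed together. A man who abstains throughout creates no partner exposure. One who resumes activity with a WOCBP at day 164 is inside the 7 months of item 6.16 and must use contraception until they end. Item 6.19 points to Appendix 2 for the choice of method, while the duration is set in items 6.15 and 6.16. This stands and narrows the consequence considerably. What remains is the man who is sexually active at entry and adopts abstinence as his way of meeting item 6.16: he has two written periods and must notice that the longer one applies.

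Other safeguards also stand. Item 6.18 requires investigators to counsel "male participants who are sexually active with WOCBP, on the importance of pregnancy prevention". Appendix 2 requires other methods to be discussed if a subject gives up abstinence, and asks that the reliability of abstinence be weighed against the subject's lifestyle. Section 10.8 asks for partner pregnancies to be reported. The consent form is not available for this review, so what men are actually told is unknown.

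**Conclusion.** The point holds as a minor contradiction. For male subjects the abstinence period in Appendix 2 is 60 days shorter than the item 6.16 formula, whatever half-life is used. It is about 50 days shorter than the rounded 7 months if the half-life is 26.7 days. The conclusion rests on reading method 7 as applying to men, which the appendix's introduction and item 6.19 support and nothing in the text excludes.

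The practical reach is small. Planned accrual includes 20 men out of 37 (section 6.7), but the number who would elect abstinence is not given, and item 6.16 continues to govern those who resume activity with a WOCBP. The 5- and 7-month periods themselves are sound. Endpoints, sample size and analysis are unaffected.

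**What to change.** Split the duration bullet under complete abstinence in Appendix 2 so that it matches the eligibility criteria:

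- **WOCBP:** throughout study treatment and for 5 months after the last dose (30 days plus about 5 half-lives), as in item 6.15.
- **Male subjects:** throughout study treatment and for 7 months after the last dose (90 days plus about 5 half-lives), as in item 6.16.

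The cost is one bullet in an appendix. No visit, procedure or analysis changes.
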